### **14. Data Collection and Reporting**

Source documents will be used to record demographic and assessment data as well as any adverse events which may occur during the study period. Source document data will be transferred to case report forms that will be submitted to the data manager. The Sponsor reserves the right to use a third-party data manager and/or electronic data capture during this study.

### **15. Confidentiality of Data**

All information and data sent to the Sponsor, Contract Research Organizations, DSMB, or the Data Manager concerning Participants or their participation in this study will be considered confidential. All data used in the analysis and reporting of this evaluation will be used in a manner without identifiable reference to the Participant. The principal investigator consents to visits by the staff of the Sponsor and its authorized representatives or any other local or national governmental body to review the study Participants' medical records including any test or laboratory data that might have been recorded on diagnostic tests media (e.g., X-rays, video, photographs, etc.).

## **16. Record Retention**

The study site is required to retain all study records required by the applicable regulations in a secure and safe facility. The study site must consult with the Sponsor before disposal of any study records, and must notify the Sponsor of any change in the location, disposition or custody of the study files. The study site must take measures to prevent accidental or premature destruction of essential documents, that is, documents that individually and collectively permit evaluation of the conduct of a study and the quality of the data produced, including paper copies of study records (e.g., patient charts) as well as any original source documents that are electronic as required by applicable regulatory requirements. All study records must be retained for at least two years after the study is completed. Participant files and other source data must be kept for the maximum period permitted by the hospital, institution or private practice, but not less than two years. These documents should be retained for a longer period, however, if required by the applicable regulatory requirements. The Sponsor must be notified and will assist with retention should study site be unable to continue maintenance of participant files for the full two years. It is the responsibility of the study site to inform the Sponsor as to when these documents no longer need to be retained.

## **17. Statistical Methods**

### **17.1 General Principles**

The primary analysis for all baseline characteristics and study outcomes will include all available data for all enrolled subjects. Standard summary statistics will be calculated for all study variables. For continuous variables, statistics will include means, standard deviations, medians and ranges. Categorical variables will be summarized in frequency distributions.

Statistical analyses will be conducted according to the principles of intent-to-treat, under which subjects will be evaluated according to their randomized assignment regardless of the treatment actually received. P-values for tests of superiority will be two-sided and for non-inferiority one-sided, with values less than 0.05 deemed statistically significant.

Statistical analyses will be conducted in SAS version 9.3 or above (SAS Institute, Cary, N.C.), R version 3.2 or above (R Foundation for Statistical Computing, Vienna, Austria, <http://www.R-project.org>) or another validated statistical software package.

### **17.2 Primary Endpoint**

The primary endpoint is change in gait speed (self-selected and fast) demonstrated during the 10MWT after 12 weeks of training, compared to baseline. Two hypotheses are associated with this endpoint; first, that the mean change in the Ekso intervention group will be statistically superior to that in the passive control group, as follows:

$$\begin{aligned} H_0: \mu_E &\leq \mu_P \\ H_A: \mu_E &> \mu_P, \end{aligned}$$

where  $\mu_E$  and  $\mu_P$  are the mean change in the Ekso and passive control groups, respectively. The hypothesis will be tested using a two-sample Student's t or Wilcoxon rank-sum depending upon normality of the trial data.

The second hypothesis is that the mean change in the Ekso intervention group will be statistically non-inferior to that in the active control group, as follows:

$$\begin{aligned} H_0: \mu_E &\leq \mu_A - \Delta \\ H_A: \mu_E &> \mu_A - \Delta, \end{aligned}$$

where  $\mu_E$  and  $\mu_A$  are the mean change in the Ekso and active control groups, respectively, and  $\Delta$  is the non-inferiority margin.  $\Delta$  is selected based upon the principles that it should be substantially less than the expected effect size comparing Ekso to passive control, and that it should represent a clinically acceptable margin of effect when differentiating Ekso from active control.

For this purpose,  $\Delta$  is therefore defined to be 0.055 m/s, which is one-half of the hypothesized treatment effect of Ekso over passive control as stated below, and one-eighth of the threshold of 0.44 m/s (1.0 mph) commonly used to represent gait speed associated with community ambulation.

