If the participant continues to meet criteria for this study the following data will be collected as *baseline data*. **NOTE: All Participant evaluations are conducted outside of Ekso, BWSTT, or BWS for overground walking. Baseline examinations may not occur more than 30 days prior to initiation of the training regimen:**

1. 10 Meter Walk Test (10MWT), at both self-selected and fast speeds
2. GAITRite Pressure Map for Temporospatial Gait Parameters (if site has one)
3. Timed Up and Go (TUG)
4. 6 Minute Walk Test (6MWT)
5. Spinal Cord Injury Functional Ambulation Inventory (SCI-FAI)
6. Walking Index for Spinal Cord Injury (WISCI II)
7. Upper and Lower Extremity Muscle Strength
8. Berg Balance Scale
9. The Spinal Cord Assessment Tool for Spastic Reflexes (SCATS)
10. Spinal Cord Independence Measure III (SCIM-III), Mobility subscale only, by interview
11. Modified Ashworth Scale
12. Spinal Cord Injury Spasticity Evaluation Tool (SCI-SET)

13. Numeric Rating Scale for spasticity
14. International SCI Quality of Life Basic Data Set
15. Epidemiological Studies Depression Scale (CES-D 10)
16. Borg Scale for maximal Rate of Perceived Exertion (collected at baseline 6MWT and at training session 1)
17. International SCI Pain Basic Data Set
18. Modified International SCI Bowel Function Basic Data Set
19. Modified International SCI Lower Urinary Tract Basic Data Set

See Appendix A for description of assessments.

The following data will be collected *per session*:

1. Any adverse events/complications (related to Participant or staff) noted following prior training session and during present session
2. Assessment of skin integrity of the anterior and posterior torso, anterior tibia, sacral area and bilateral feet (before and after training)
3. Walk time\*
4. Stand time\*
5. Seated rest time
6. Number of steps total and in each mode\* or number of steps at each BWS%
7. Time spent in each mode\* or time spent at each BWS%
8. Any equipment used for training, including type of assistive device and braces
9. Number of therapists/staff required at each training session to ensure the safety of the Participant and to complete the training session goals
10. Amount of assistance (e.g. min, mod, max) as reported by staff members at each training position (hips, trunk, right LE, left LE, etc.)

\* For Group 1 Participants, these data are *automatically collected* by Ekso (in Ekso Pulse) at the end of each training session

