This study design involves outcome variables measured on binomial, ordinal, and continuous scales. For the continuously scaled outcome variables (i.e., 10MWT, 6MWT, WISC-II Score, etc.), the general situation applies analysis of variance and covariance when there are  $g$  distinct groups with a sample of observations for each group. The general null hypothesis is that the outcome variable distribution is the same for the treatment and the active control group. The assumptions associated with the analysis of variance are: 1) the  $g$  samples are independent random samples, 2) the observations in group  $i$  (for each  $i = 1, 2, \dots, g$ ) are a random sample from a normal probability distribution with mean  $\mu_i$  and variance  $\sigma_i^2$ , and 3) the  $g$  population variances,  $\sigma_1^2, \dots, \sigma_g^2$ , are equal to a common variance  $\sigma^2$ . Inherent to these assumptions is the assumption of a linear additive model with equal sample sizes. There are a variety of statistical procedures for the comparison of means in an analysis of variance setting. In the case of unequal sample sizes and multiple endpoints, the Scheffe's or Bonferroni procedures are appropriate to control for experiment-wise multi-comparison error (Woolson, 1983). If the assumption of normal distributions is not met, rank analysis of variance is used. More common rank analysis of variance tests are Kruskal-Wallis and Friedman tests. In addition, paired t-Test will be used for paired data since this is a single group matched-pairs design with the assumption that the pairwise differences are normally distributed.

Multiple comparison analysis (repeated measures) of ordinal or nominal-scale data (i.e., 5-point Likert type scales, numeric rating scales, etc.) generally assumes a logit model. This type of model uses cumulative logits, which automatically take the ordinality of the data into account. If the assumptions associated with this model are met, tests of uniform association and proportional odds can be computed. If, however, maximum likelihood estimation is desirable, generalized logits are computed from a log-linear model (Agresti, 1990 and Stokes et al., 1995).

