### 1.3 Primary Endpoint

*Efficacy:* The primary endpoint is the mean increase in gait speed demonstrated during the 10MWT after 12 weeks/36 sessions of training compared to baseline and compared between groups. Both self-selected and fast speeds will be performed on the 10MWT, with the fast speed taking precedent.

Hypothesis #1: The mean change in the Ekso G intervention group will be statistically superior to that in the passive control group, as follows:

$$H_0: \mu_E \leq \mu_p \text{ vs } H_a: \mu_E > \mu_p$$

where  $\mu_E$  and  $\mu_p$  are the mean change in the Ekso G intervention group and the passive control group, respectively.

Hypothesis #2: Using the two one-sided (TOST) procedure, the null hypothesis of non-equivalence or non-inferiority of means will be tested for the Ekso GT ( $\mu_E$ ) versus the Active Control ( $\mu_A$ ) using a two-group design with equal sample sizes in the two groups. We want to demonstrate that the mean gait speeds will have similar distributions on the average for the two intervention groups. We specify that the practical difference in means is therefore defined to be 0.055 m/s, which is one-half of the hypothesized treatment effect of Ekso G over passive control as stated below, and one-eighth of the threshold of 0.44 m/s (1.0 mph) commonly used to represent gait speed associated with community ambulation. The two null hypotheses are specified below:

$$H_{01}: \mu_E - \mu_A \leq \delta_L \text{ or } H_{01}: \mu_E - \mu_A + \delta_U \leq 0 \text{ vs } H_{02}: \mu_E - \mu_A \geq \delta_L \text{ or } H_{02}: \mu_E - \mu_A - \delta_U \geq 0$$

The composite null hypothesis is that the two groups have unequal mean gait speeds. The alternative hypothesis is that the mean gait speeds are equivalent for both the Ekso G Intervention group and the active control group.

Reject  $H_{01}$  if the observed difference in the two means is too large. That is, reject if the lower bound for two-sided  $100(1-2\alpha)\%$  confidence interval for  $\mu_E - \mu_A$  is greater than the group mean multiplied by the assumed practical difference of 0.055 m/s.

Reject  $H_{02}$  if the observed difference in means is too small. That is, reject if the upper bound for the two-sided  $100(1-2\alpha)\%$  confidence interval for  $\mu_E - \mu_A$  is less than the group mean multiplied by the assumed practical difference of 0.055 m/s.

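### Neither primary hypothesis has a baseline-adjusted model, although baseline fast walking speed is collected; specifying one is a low-cost efficiency gain

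*Protocol*

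**What the plan says.** Protocol 17.2 defines the primary endpoint as change in gait speed "demonstrated during the 10MWT after 12 weeks of training, compared to baseline". SAP 1.3 describes it as the increase "after 12 weeks/36 sessions of training compared to baseline and compared between groups". Protocol section 4 and SAP 1.3 both give the fast pace precedence over the self-selected pace.

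For superiority of Ekso over passive control, Protocol 17.2 says: "The hypothesis will be tested using a two-sample Student's t or Wilcoxon rank-sum", the choice between the two resting on whether the data look normal. It names no test procedure for non-inferiority to active control. SAP 1.3 handles that comparison with two one-sided tests, read from a confidence interval for the difference in means. Neither text includes a covariate.

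SAP 1.1 says that for continuous outcomes, with the 10MWT as its first example, "the general situation applies analysis of variance and covariance". It names no covariate and does not tie the sentence to Hypothesis #1 or #2.

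The baseline list in Protocol section 11 includes "10 Meter Walk Test (10MWT), at both self-selected and fast speeds". Protocol 8.2 describes computer randomization at 2:2:1 and mentions no stratification by speed.

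**The concern.** The baseline value of the primary variable is measured in every arm, yet the plan uses it only to form a difference. If slower and faster walkers change by different amounts, baseline explains part of the variance of change, and an unadjusted test leaves that part in the error term. The plan also aims for only 80% power, with 19 evaluable participants in the passive arm. Chance differences in baseline speed are then not negligible, and subtraction removes them completely only if week-12 speed rises one-for-one with baseline speed.

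Two things are at stake: some power in both primary comparisons, and a part of any baseline imbalance that stays in the estimate. It is also unclear which model is primary, because SAP 1.1 points towards covariance analysis while Protocol 17.2 and SAP 1.3 do not.

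**Working it through.** **Inputs** (Protocol 17.1, 17.2 and 17.4; SAP 1.8). Mean change is 0.11 m/s for Ekso, 0.078 for active control and 0 for passive control. The SDs of change are 0.18, 0.108 and 0.108. The margin is 0.055 m/s. Alpha is 0.05, two-sided for superiority and one-sided for non-inferiority. Evaluable numbers are 38/38/19.

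**Step 1: the plan's own figures.** Unequal-variance (Welch) t test, power from the noncentral t.
- Superiority: SE = √(0.18²/38 + 0.108²/19) = 0.0383. Noncentrality = 0.11/0.0383 = 2.87, df = 53, power 80.5%. The smallest 2:1 design reaching 80% is 38/19, as stated.
- Non-inferiority: distance to the margin = 0.055 + (0.11 − 0.078) = 0.087. At 37 per arm power is 80.2%, so the stated 37 reproduces. At 38 per arm SE = √((0.18² + 0.108²)/38) = 0.0341, noncentrality = 2.55, power 81.1%.

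**Step 2: the effect of baseline adjustment.** Adjustment multiplies the variance of change by 1 − r², where r is the baseline-change correlation. The documents give no r. The table assumes one value for all arms. The robust columns come from simulating the three-arm model (SDs as planned, HC3 standard errors, 8,000 runs, Monte Carlo error about 0.4 points).

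| r (assumed) | 1 − r² | Superiority 38/19, analytic | Superiority, robust | Non-inferiority 38/38, analytic | Non-inferiority, robust |
|---|---|---|---|---|---|
| 0 | 1.00 | 80.5% | 79.3% | 81.1% | 80.3% |
| 0.2 | 0.96 | 82.1% | not run | 82.5% | not run |
| 0.3 | 0.91 | 84.0% | 82.3% | 84.2% | 82.9% |
| 0.4 | 0.84 | 86.8% | 85.1% | 86.7% | 85.0% |
| 0.5 | 0.75 | 90.3% | 88.9% | 89.8% | 88.6% |

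If baseline and week-12 variances are equal and their correlation is rho, then 1 − r² = (1 + rho)/2. With rho = 0.9 the factor is 0.95 and superiority power is 82.5%. With rho = 0.5 the factor is 0.75 and power is 90.3%.

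**Step 3: unequal slopes.** The common-r assumption matters. In simulation with r = 0.3 in Ekso and 0 in both controls, superiority power hardly moved (81.3% unadjusted, 81.9% adjusted with HC1 errors). With r = 0.3 in Ekso and active control and −0.3 in passive control, it fell from 80.3% to 79.0% with HC1 errors, and from 81.2% to 77.1% with HC3.

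**Step 4: imbalance left by the change score.** If beta is the slope of week-12 speed on baseline speed, the error left is (beta − 1) × baseline difference. Assume a baseline SD of 0.127 m/s, that is 0.44/√12, a uniform spread over 0 to 0.44.
- Ekso versus passive: a one-SE difference is 0.127 × √(1/38 + 1/19) = 0.036 m/s. The error is 0.018, 0.011 or 0.004 m/s in size for beta of 0.5, 0.7 or 0.9, against a postulated effect of 0.11.
- Ekso versus active: a one-SE difference is 0.127 × √(2/38) = 0.029 m/s. The errors are 0.015, 0.009 and 0.003, against a margin of 0.055.

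The 0.44 limit applies to self-selected speed, so fast speed may vary more. With an assumed SD of 0.20 the beta = 0.5 errors become 0.028 and 0.023 m/s. At beta = 1 they are zero.

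**The case against.** A reader might infer that the primary test ignores baseline speed and leaves imbalance uncorrected. The documents do not support that. Both define the endpoint relative to baseline, so subtraction already corrects imbalance with a slope of 1, and only the (beta − 1) part remains. Regression to the mean is no evidence of bias either: under randomization it affects all arms equally in expectation and only adds variance, which step 2 already counts.

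A reader might also infer that the trial is underpowered for want of a covariate. It is not: on the plan's inputs 38/19 and 37 per arm reach 80% without one. If all 127 were enrolled and evaluable, an unadjusted Welch comparison at about 51/25 would have about 90% superiority power.

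The strongest remaining objection is that the gain is conditional. No correlation is given, weak correlations yield little, and a common-slope model can lose power when slopes differ between arms. This stands, and it limits the claim.

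A further caution concerns the starting point. The 80.5% belongs to Welch's test. If the named Student's t is read as the pooled-variance test, superiority power at 38/19 is about 67% by calculation and about 70% by simulation. That gap exceeds the covariate gain over most of the range shown. It is a separate matter, but it means the table should not be read as the gain over a pooled t test.

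Finally, SAP 1.1 might be taken to mean that covariance analysis is already planned. With no covariate named and no link to either hypothesis, it does not settle the primary model.

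**Conclusion.** The point holds as an efficiency improvement and a gap in specification, not as an error. Neither primary hypothesis has a baseline-adjusted model, and the two documents do not state one common primary model. The unadjusted comparison is valid.

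If r is the same in all arms, the analytic gain in superiority power is 1.6 points at r = 0.2 (82.1 − 80.5), 3.5 at 0.3 and 9.8 at 0.5. For non-inferiority it is 1.4, 3.1 and 8.7 points. Robust errors reduce these by about 1 to 2 points. The downside is about 1 point at r = 0, and roughly 1 to 4 points of superiority power in the simulated case where the passive slope has the opposite sign. The non-inferiority figures also rest on the plan's assumed 0.032 m/s advantage of Ekso over active control. The absence of a covariate is certain; the size of the gain is not, because r, rho, beta and the baseline SD are all assumptions.

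**What to change.** In Protocol 17.2 and SAP 1.3, before unblinding, name one primary model for both hypotheses: week-12 change in fast 10MWT speed on arm and baseline fast speed, using the same baseline value that is subtracted to form the change. Specify heteroscedasticity-robust standard errors and their type, since the planned SDs are 0.18 and 0.108. Read the Ekso-passive contrast against 0 and the Ekso-active contrast against −0.055 m/s. Keep the unadjusted Welch comparison as a sensitivity analysis, and align the general sentence in SAP 1.1 with this model.

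The cost is wording only, with no new data or participants. The statistical price is about 1 point of power if baseline is unrelated to change, and a few points if slopes run in opposite directions between arms.

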### 17.4 Sample Size

Computations for sample size and power are based on effect sizes derived from internal study data and the relevant clinical literature for the primary endpoint. For the Ekso intervention group, the postulated effect (derived from internal study data) is a mean change from baseline in gait speed of 0.11 m/s, with a corresponding standard deviation of 0.18 m/s. For the active control group, the postulated effect is a mean change from baseline in gait speed of 0.078 m/s (derived from the relevant clinical literature), with a corresponding standard deviation of 0.108 m/s.

The passive control group is postulated to have a mean change of zero with the same standard deviation as active control, or 0.108 m/s. Sample size and power are then computed for both statistical tests cited above: superiority of Ekso to passive control and non-inferiority of Ekso to active control.

Under 2:2:1 randomization with a desired power of 80%, the required sample size for superiority of Ekso intervention to passive control is 38 subjects with evaluable data in the Ekso group and 19 in passive control (incorporating the 2:1 Ekso: passive control randomization). For non-inferiority of Ekso to active control, the groups are of equal size and the required sample size is 37 per group.

Taking the greater of these numbers for each randomized group, total sample size under 2:2:1 randomization is therefore 38 for Ekso intervention, 38 for active control and 19 for passive control, a total of 95. To account for possible attrition as well as potential variance from the postulated effects, up to 127 subjects in the randomized group will be enrolled.

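### The test of the first primary hypothesis (Ekso vs passive control, stated in means) is left to an undefined normality check, and neither candidate test matches the unequal-variance calculation behind the sample size

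*Protocol*

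**What the plan says.** Protocol 17.2 sets two hypotheses on change in 10MWT gait speed at 12 weeks. The first is that "the mean change in the Ekso intervention group will be statistically superior to that in the passive control group", with H0: μE ≤ μP. The next sentence gives its test: Student's t or the "Wilcoxon rank-sum depending upon normality of the trial data". That sentence comes before the second hypothesis (non-inferiority to active control) and refers to a single hypothesis.

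The protocol does not say which normality test is used, at what threshold, on what (each group or pooled residuals), or whether the check is done blinded.

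SAP 1.3 restates the first hypothesis in means and names no test for it. SAP 1.1 describes analysis of variance with a common variance for continuous outcomes in general, and adds: "If the assumption of normal distributions is not met, rank analysis of variance is used". For the second hypothesis, SAP 1.3 specifies two one-sided tests on the difference in means.

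On error rates, Protocol 17.1 says: "P-values for tests of superiority will be two-sided and for non-inferiority one-sided, with values less than 0.05 deemed statistically significant". The sample size (Protocol 17.4, repeated in SAP 1.8) assumes for Ekso a "mean change from baseline in gait speed of 0.11 m/s, with a corresponding standard deviation of 0.18 m/s". For the comparator: "The passive control group is postulated to have a mean change of zero with the same standard deviation as active control, or 0.108 m/s".

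**The concern.** The hypothesis is about means, but the outcome data decide whether means are tested. A rank-sum test compares the two distributions through P(X > Y). It speaks to a shift in location only when the groups have the same shape and spread. The plan postulates an Ekso SD 1.67 times that of passive control (0.18/0.108), so by its own assumptions that condition fails. If the data are also skewed, which is when the rule would switch, the rank test can reject although the means are equal.

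Because the criterion is undefined, two analysts could both follow the protocol and report different p-values for a primary hypothesis.

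A second mismatch sits in the same sentence. Student's t, the test used if the data look normal, pools the variances, while the sample size was computed with separate SDs. With 2:1 allocation and the larger SD in the larger group, pooling overstates the standard error and costs power.

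**Working it through.** **Inputs** (Protocol 17.1, 17.2, 17.4): mean change 0.11 vs 0; SD 0.18 vs 0.108; n = 38 vs 19; two-sided 0.05; target power 80%.

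**1. Reproducing the stated size.** With separate variances:

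- SE = √(0.18²/38 + 0.108²/19) = √(0.000853 + 0.000614) = 0.0383; 0.11/0.0383 = 2.87.
- Normal approximation: Φ(2.87 − 1.96) = 81.9%. At 36/18 it is 79.8%.
- Welch t (about 53 df, noncentral t): 80.5%. At 36/18 it is 78.3%.

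So 38/19 is the smallest 2:1 size that reaches 80% by either route. Pooled-variance formulas do not return it. An equal-weight pooled SD of 0.148 gives 44/22, and the df-weighted SD of 0.160 gives 50/25. One-sided 0.05 with separate variances gives 30/15.

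**2. The two named tests under the plan's own assumptions.** Pooled variance = (37 × 0.18² + 18 × 0.108²)/55 = 0.0256, so SD = 0.160 and pooled SE = 0.160 × √(1/38 + 1/19) = 0.0450, against the correct 0.0383. Simulated power at 38/19 with normal data is about 70% for Student's t, 72% for Wilcoxon and 80% to 81% for Welch. Student's t passes 80% at about 48/24.

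**3. The switching rule.** The documents give neither a criterion nor a skewness, so both are assumed here. Wilcoxon is used if Shapiro-Wilk gives p < 0.05 in either group, otherwise Student's t. Change scores are shifted gamma variables (shape 4 for skewness 1, shape 1 for skewness 2), or their mirror images for left skew, scaled to the plan's SDs. There are 20,000 trials per row and mean difference, at 38/19. Figures in brackets are rejections in favour of Ekso.

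| Shape of change scores | Rank test chosen | Equal means: rule rejects | Equal means: Welch rejects | Power at 0.11: rule | Wilcoxon alone | Welch |
|---|---|---|---|---|---|---|
| Normal | 10% | 2.5% (1.3%) | 5.0% (2.4%) | 70% | 72% | 80% |
| Right skew 1, both groups | 68% | 5.1% (0.6%) | 4.9% (2.3%) | 70% | 68% | 81% |
| Right skew 1, Ekso only | 58% | 5.9% (0.4%) | 5.3% (1.9%) | 65% | 61% | 82% |
| Right skew 2, both groups | >99% | 13.8% (0.1%) | 4.7% (2.1%) | 85% | 85% | 81% |
| Right skew 2, Ekso only | 99% | 13.5% (0.1%) | 5.2% (1.4%) | 61% | 61% | 84% |
| Left skew 1, both groups | 67% | 4.9% (4.3%) | 4.8% (2.4%) | 83% | 86% | 80% |
| Left skew 1, Ekso only | 58% | 5.8% (5.3%) | 5.2% (3.3%) | 81% | 85% | 79% |
| Left skew 2, both groups | >99% | 13.9% (13.8%) | 4.4% (2.3%) | 96% | 96% | 80% |
| Left skew 2, Ekso only | 99% | 13.5% (13.3%) | 5.1% (3.6%) | 94% | 94% | 78% |

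The mechanism shows in P(X > Y). With right skew 2 in both groups and equal means it is 0.42 rather than 0.50, so the rank test is detecting a real difference that is not a difference in means.

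**4. Without the unequal spread.** If both groups share one distribution, the mechanical rule rejects in 4.9% to 5.1% of trials. If the analyst could take the smaller of the two p-values, which the undefined criterion does not exclude, the rate is 6.0% to 6.8%.

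**The case against.** The rule is written in advance and confined to two familiar tests, and SAP 1.1 also plans distribution diagnostics and robust methods. Pre-testing as such does little harm here: when the two distributions are equal, a mechanical rule holds its level. The large departures need strong skew and unequal spread together. All of this stands, and it limits the size of the point.

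A reader might infer three stronger things that the documents do not support.

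- *That the switch also undermines the non-inferiority test because a rank test ignores the 0.055 m/s margin.* The protocol's sentence belongs to the first hypothesis only. SAP 1.3 tests the second on means, with a confidence interval and the margin. The rank sentence in SAP 1.1 is general text for continuous outcomes.
- *That switching to Wilcoxon costs power.* Against the plan's own alternative, Student's t, it does not with normal data (72% vs 70%). The gap to 80% comes from pooling unequal variances. With skewed data Wilcoxon lies below or above Welch depending on the direction of the skew and on which groups have it.
- *That the rule inflates false claims of benefit.* With right skew the excess rejections go against Ekso, and false claims for Ekso fall below the nominal 2.5%. Only left skew produces false claims for Ekso above that level.

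**Conclusion.** The point holds for hypothesis 1. As written, the plan states a hypothesis in means and may test something else, on a criterion it does not define, and the SAP does not settle the choice.

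Two results need no assumption beyond normality and the plan's own figures: 38/19 reproduces as a two-sided unequal-variance comparison of means, and neither named test reaches 80% power at that size.

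The error-rate result rests on an assumed criterion and an assumed skewness of 1 to 2. Within that range, rejection at equal means runs from about 5% to 14%, with the direction set by the sign of the skew. At skewness 1 the total rate is close to 5%, so the large figures belong to strong skew. No general loss or gain of power can be claimed. The stated sample size is not itself wrong; it belongs to a test that the plan does not name.

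**What to change.** In Protocol 17.2 and SAP 1.1 and 1.3, delete the normality-dependent choice for hypothesis 1. Name one mean-based primary test to be used whatever the distribution looks like: the unequal-variance (Welch) t, or ANCOVA with robust standard errors, with covariates and variance estimator stated. Report Wilcoxon as a sensitivity analysis, described as a comparison of distributions. Hypothesis 2 needs no change on this account.

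The cost is a few sentences. Welch's t keeps 80.5% power at 38/19 under the plan's assumptions, so neither the evaluable total of 95 nor the cap of 127 has to change. Make the amendment before anyone sees outcome data by group.
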